6.9 Intervention After the End of the Study

No intervention will follow the end of the study. Decision to continue on Szc treatment or SoC will be at investigator's discretion.

7 DISCONTINUATION OF STUDY INTERVENTION AND PARTICIPANT DISCONTINUATION/WITHDRAWAL

7.1 Discontinuation of Study Intervention

7.1.1 Permanent Discontinuation of Study Intervention

It may be necessary for a participant to permanently discontinue (definitive discontinuation) study intervention. If study intervention is permanently discontinued, the participant will be followed up according to the SoA ([Table 1](#)). See the SoA for data to be collected at the time of discontinuation of study intervention and follow-up for any further evaluations that need to be completed.

To minimize risk for events related to severe hypokalaemia, the following discontinuation criterion will be followed:

- Confirmed $K^+ < 3.0$ mmol/L by taking a second measurement after a ≥ 10 -minute interval, at any time during the study, the participant should immediately receive appropriate medical intervention and study intervention should be permanently discontinued.

To minimize risk for events related to severe HK, the following discontinuation criterion will be followed:

- Confirmed $K^+ > 6.0$ mmol/L by taking a second measurement after a ≥ 10 -minute interval, at any time during the study, the participant should immediately receive appropriate medical intervention and study intervention should be permanently discontinued.

To minimize risk for events related to prolongation of QT interval corrected (QTc), the following discontinuation criteria will be followed:

- If an absolute QTc > 550 ms, or an increase in QTc interval > 60 ms from baseline to more than 500 ms is reached, the participant should immediately receive appropriate medical intervention and be permanently discontinued from the study intervention. The QTcF algorithm is recommended. All participants meeting the QTc > 500 ms criterion should immediately have K^+ assessed, if not already done within 1 hour of performing the electrocardiogram (ECG).

For serious arrhythmia (eg, associated with $K^+ < 3.5$ or > 5.6 mmol/L), study drug should be permanently discontinued.

Other reasons for discontinuation of study intervention may include:

- Participant decision; the participant is at any time free to discontinue treatment, without prejudice to further treatment.
- Incorrectly randomised participant, in whom the inclusion/exclusion criteria violation would put the participant at undue risk. This will require a discussion with the medical team, who will provide a final outcome / action.
- Adverse event for which the investigator judges continued treatment may put the participant at undue risk.
- Severe noncompliance with the clinical study protocol (CSP)
- Pregnancy (see Section 8.3.8).

For discontinuation pertaining to COVID-19, please see [Appendix C](#).

Note that discontinuation from study intervention is NOT the same as a withdrawal from the study.

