4 STUDY DESIGN

4.1 Overall Design

- This is a Phase 4, randomised, controlled, open-label, parallel-group, multicentre study in participants with CKD treated for HK whilst in hospital.
- Participants from 30 to 50 sites in 4 to 7 countries will be screened for enrolment. Assuming a 20% drop out rate from enrolment to randomisation and a 20% drop out post-discharge (post-randomisation), approximately 163 participants will have to be enrolled to achieve 104 evaluable participants (52 per arm). In total, up to a maximum of 163 participants will be enrolled, resulting in approximately 130 participants discharged and randomised and 104 evaluable participants (52 per arm).
- The study plans to enrol approximately equal numbers of participants with mild HK (K^+ between > 5.0 and ≤ 5.5 mmol/L) and with moderate/severe HK (K^+ between > 5.5 and ≤ 6.5 mmol/L), with a minimum of 30% of the enrolled participants in either group.
- During the in-hospital phase, participants will be treated with SZC as per local label (correction and/or maintenance treatment, see Section 6.1), starting at baseline and based on local K^+ measurement obtained within 24 hours of treatment initiation:
 - Participants with HK (K^+ between > 5.0 and ≤ 6.5 mmol/L): 1) stop current K-binder if any, 2) start SZC correction dose (note: participants currently on SZC should continue SZC correction dose, up to 72 hours).
 - Participants currently receiving any treatment for the current episode of HK and are already NK at baseline ($K^+ \leq 5.0$ mmol/L): 1) stop any current K-binder, 2) start SZC maintenance dose (note: participants currently on SZC maintenance dose should continue SZC maintenance dose).
 - All treatment decisions, including modification of the ongoing therapy for HK, must be based on the investigator's medical judgement of the participant's best interest.
- At discharge, NK participants who have been treated with SZC for between 1 and 21 days whilst in hospital and are started on SZC maintenance dose will be randomised in a 1:1 ratio to one of the following arms:
 - Arm A: Participants discharged with SZC, as per local label, to manage HK until the end of the outpatient phase
 - Arm B: Participants discharged with SoC, as per local practice, to manage HK until the end of study.

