5 STUDY POPULATION

Prospective approval of protocol deviations to recruitment and enrolment criteria, also known as protocol waivers or exemptions, is not permitted. Rescreening of participants is allowed as detailed in Section [5.4](#).

The distribution of participants across the range of K^+ levels will be operationally controlled by ensuring that the following ratios are met:

- Approximately 50% enrolled participants with mild HK (K^+ between > 5.0 and ≤ 5.5 mmol/L) and approximately 50% with moderate/severe HK (K^+ between > 5.5 and ≤ 6.5 mmol/L)
- A minimum of 30% of enrolled participants in each group.

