6.1 Screening and Inpatient Phase

Participants with HK (see inclusion criterion #4) and not on SZC or patiromer before this current ED visit/hospital admission (initiation of SZC or patiromer during ED visit/hospitalisation preceding enrolment is allowed), will start SZC, as per local label, during the inpatient phase. Initiation of SZC treatment will be based on local measurement of K⁺, obtained within 24 hours prior to first dose of on-study SZC:

- Correction treatment: 10 g, TID for up to 72 hours. Typically, NK is achieved within 24 to 48 hours. If participants are still hyperkalaemic after 48 hours of treatment, the same regimen can be continued for an additional 24 hours. If NK is not achieved after 72 hours of treatment, other treatment approaches should be considered, and the participant discontinued from the study due to lack of SZC effect. Participants who received any HK treatment during current ED visit/hospitalisation preceding enrolment and are NK at baseline can directly start the maintenance dose of SZC (see hereafter).
- Maintenance treatment (once NK [K^+ between 3.5 and 5.0 mmol/L, inclusive] is reached): 5 g, QD. Dose will be adjusted based on K^+ (see [Table 4](#)). The recommended maintenance dose range is from 5 g every other day to 10 g daily.

Participants with NK and who have been started on a maintenance dose for SZC (per local label) at the time of discharge will be randomised at discharge to either Arm A (SZC per local label) or Arm B (SoC, as per local practice) and enter the outpatient phase.

The following participants will not be eligible for randomisation:

- Participant intended to be discharged on a K-binder as per the site routine medical practice (discontinued from the study)
- Participant with an in-hospital phase exceeding 21 days (including screening), except when study medical monitor's approval was sought for longer duration of hospital stays for specific participants
- Participants with $K^+ > 5.0$ mmol/L at discharge; these participants will be discontinued from the study treatment and followed up as per protocol
- Participants with $K^+ < 3.5$ mmol/L at discharge; these participants will be discontinued from study treatment and will be followed per protocol.

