6.2 Outpatient Phase

Participants randomised to Arm A will be discharged with SZC dosed per local label (from 5 g every other day to 10 g daily) to manage K^+ until the EOT (180 days post-discharge).

As per label, SZC dose titration will be allowed based on K^+ levels as detailed in [Table 4](#).

Table 4 Dose Titration and Discontinuation Criteria During the Outpatient Phase

K^+ (mmol/L)	Dose Titration and Discontinuation Criteria for Abnormal K^+
< 3.0	
• Treatment permanently discontinued (see Section 7.1.1). Check ECG and treat according to medical judgment.
3.0 - 3.4	
• Check ECG, permanently discontinue treatment if serious arrhythmia found and treat according to medical judgment.

K⁺ (mmol/L)	Dose Titration and Discontinuation Criteria for Abnormal K⁺
	
 • If no serious arrhythmia found, investigator to consider to down-titrate^a or pause SZC and treat according to medical judgment. Participants with heart failure should pause study drug. • Increase monitoring until K⁺ \geq 3.5 mmol/L.^a • Evaluate for underlying risk for hypokalaemia. If hypokalaemia resolves and participant deemed appropriate to restart treatment (for participants who have paused SZC), then the investigator should consider to restart SZC at a lower dose.^a
3.5 - 5.0	
 • No change in SZC dose is recommended.
5.1 – 5.5	
 • Increase SZC dose by 5 g QD increments up to a maximum of 10 g QD.^a • Increase monitoring until K⁺ in normal range.
5.6 – 6.0	
 • Check ECG, discontinue treatment if serious arrhythmia found and treat according to medical judgment. • If no serious arrhythmia, increase SZC dose by 5 g QD increments up to a maximum of 10 g QD.^a • Further K⁺ monitoring and treatment per investigator medical judgment based on participant risk and benefit. • Increase monitoring frequency until K⁺ in normal range.
> 6.0	
 • Treatment permanently discontinued (see Section 7.1.1); initiate rescue therapy (see Section 6.7.1 for rescue therapy). • Check ECG and treat according to medical judgment.

Abbreviations: ECG = electrocardiogram; K⁺ = potassium; QD = once daily; RAASi = renin angiotensin-aldosterone system inhibitor; SZC = sodium zirconium cyclosilicate.

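### The permanent stop for a confirmed K+ above 6.0 mmol/L has no phase limit, so it contradicts entry up to 6.5 mmol/L followed by in-hospital correction treatment

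*Protocol*

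**What the plan says.** **The stopping rule.** Protocol Section 7.1.1 has two K+ criteria, one below 3.0 and one above 6.0 mmol/L. Both end in the same words: "at any time during the study, the participant should immediately receive appropriate medical intervention and study intervention should be permanently discontinued". This point concerns only the second. Confirmation means a second measurement at least 10 minutes after the first. Neither criterion is limited to a study phase.

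**Entry and in-hospital treatment.** Inclusion criterion 4 accepts a hyperkalaemic local value up to 6.5 mmol/L. Section 5 plans "approximately 50% with moderate/severe HK", defined as above 5.5 and up to 6.5 mmol/L, and sets a floor: "A minimum of 30% of enrolled participants in each group". For baseline K+ above 5.0 and up to 6.5 mmol/L, Section 4.1 instructs sites to "1) stop current K-binder if any, 2) start SZC correction dose". Section 6.1 gives the regimen as "Correction treatment: 10 g, TID for up to 72 hours" and adds: "If participants are still hyperkalaemic after 48 hours of treatment, the same regimen can be continued for an additional 24 hours". Its stop is based on time: "If NK is not achieved after 72 hours of treatment, other treatment approaches should be considered", with the participant then discontinued from the study.

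**Table 4.** The table in Section 6.2 has a row for K+ above 6.0 that also requires permanent discontinuation and refers to Section 7.1.1. It is titled "Dose Titration and Discontinuation Criteria During the Outpatient Phase", but Section 6.1 also sends in-hospital maintenance dosing to it.

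**Randomisation.** Section 6.1 requires a participant to be normokalaemic and started on maintenance SZC at discharge.

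**The concern.** A site treating a participant who entered above 6.0 mmol/L and whose repeat value is still above 6.0 has two instructions. Sections 4.1 and 6.1 say to start or continue correction. Section 7.1.1, read literally, says to end study intervention for good. Both cannot be followed.

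The choice affects the analysis as well as care. A participant stopped permanently during correction cannot reach maintenance SZC and so cannot enter the randomised comparison. Who is randomised at the upper end of the entry range therefore depends on which section a site follows. A site could also be recorded as deviating from the protocol whichever section it follows.

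**Working it through.** The plan gives no figure for this point, so the first part of the check sets the rules side by side.

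1. *Does Section 7.1.1 cover in-hospital SZC?* Yes. Table 1 lists in-hospital dispensing as study intervention, Section 6.3.1 includes daily inpatient dispensing, and SAP Section 3.3.1 dates Day 1 of the in-hospital phase from the first dose of SZC as study intervention.
2. *Where do the rules overlap?* Entry and correction cover above 5.0 to 6.5 mmol/L; the stopping rule covers everything above 6.0. The overlap at entry is above 6.0 to 6.5 mmol/L.
3. *Can a confirmed value arise there?* Yes. Footnote i to Table 1 requires K+ at least once a day during correction, and the value may be checked more often.
4. *Does any other text limit the rule?* No. The investigator-judgement clause in Section 4.1 does not mention Section 7.1.1, and Section 8 allows no waivers or exemptions. The outpatient title of Table 4 limits the table, not Section 7.1.1.
5. *Who is outside the conflict?* A participant with a single value above 6.0 before the first dose, because the rule needs a second measurement and treatment has not begun. Also a participant already normokalaemic at baseline, who goes directly to maintenance and does not meet the rule at entry.

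**Size.** The inputs are 163 enrolled (Section 4.1), a planned share of 50% and a minimum of 30% in the moderate/severe group (Section 5), and an assumed 20-40% of that group above 6.0. The documents do not give this last share.

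Upper bound = enrolled × stratum share × share above 6.0.

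- At the planned 50%: 163 × 0.50 × 0.20 = 16.3 and 163 × 0.50 × 0.40 = 32.6, so 16-33.
- At the 30% minimum: 163 × 0.30 × 0.20 = 9.8 and 163 × 0.30 × 0.40 = 19.6, so about 10-20.

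These figures count everyone in the band. The number in conflict is the part of them with a confirmed value above 6.0 at baseline or during correction, which the documents do not let one estimate.

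**The case against.** The best defence is that the protocol can be read coherently. Correction has its own time-based stop at 72 hours. Table 4 governs maintenance, in hospital through Section 6.1 and after discharge through its title, and its row above 6.0 points to Section 7.1.1. On that reading the criterion applies only once normokalaemia has been reached. This may be what was meant, and it narrows the problem to correction treatment. But Section 7.1.1 does not say so, and its scope is the whole study.

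The defence can add that few participants may be caught. Section 4.3 reports K+ falling as early as 1 hour after a dose, larger falls from higher baseline values, and normokalaemia in most participants within 24 to 48 hours. That stands, and it is why the count is only a ceiling.

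Four stronger inferences are tempting, and the documents do not support them.

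- *That everyone enrolled above 6.0 meets the rule at or just after the first dose.* The confirmation requirement prevents this, and the first mandated on-treatment value may come up to a day later.
- *That the whole in-hospital phase is in conflict.* In-hospital maintenance is already referred to Table 4, which has the same threshold.
- *That sites will in fact act differently.* The text permits it, but nothing in the documents shows it.
- *That the rule depletes a planned subgroup.* The band above 6.0 to 6.5 appears in SAP Sections 4.2.2.6 and 4.2.3.7 only as an alternative categorisation, run with 10 or more events per category. Taking 16.3-32.6 participants less the planned 20% loss before randomisation leaves 13-26. At the planned mean event rate of (17% + 43.2%) / 2 = 30.1%, that is about 4-8 events for the main secondary endpoint, below the threshold even without the conflict. For the primary endpoint, with a planned mean response of (0.88 + 0.59) / 2 = 0.735, it is about 10-19 responders, so the subgroup might run. The argument is too weak to carry the point.

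**Conclusion.** The contradiction is real and lies in correction treatment. For K+ above 6.0 mmol/L confirmed by a second measurement at baseline or during correction, Section 7.1.1 requires a permanent stop where criterion 4 and Sections 4.1 and 6.1 allow treatment to start and continue. Followed literally, the stop also keeps those participants out of randomisation.

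This conclusion rests on the wording alone and needs no assumption about numbers. The size does need one: the 16-33 (or 10-20) is a ceiling that depends on the assumed 20-40% share and on every participant in the band having a confirmed value. The actual number could be near 0. The documents do not settle which rule was intended, and this review takes no position on which is clinically right.

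**What to change.** Reconcile Section 7.1.1, inclusion criterion 4, Sections 4.1 and 6.1, and Table 4. Each should state whether the criterion for K+ above 6.0 mmol/L applies during correction treatment, in-hospital maintenance, the outpatient phase, or all of these. A split into in-hospital and outpatient alone is not enough, because Section 6.1 already refers in-hospital maintenance to Table 4; the text must separate correction from maintenance. The title of Table 4 should agree with that use. Which rule applies in each period is for the sponsor's clinical team to decide.

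The cost is a protocol clarification. It needs no additional data and no change to the sample size or the analysis.

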7.1.2 Temporary Discontinuation

If K^+ ranges from 3.0 to 3.4 mmol/L, the investigator will consider SZC administration to be either down-titrated or paused and hypokalaemia should be managed as per standard practice. Participants with heart failure should pause study drug. The participant should be evaluated for any risk factors for hypokalaemia, including any intercurrent illness or comorbidity. Sodium zirconium cyclosilicate administration can be resumed (if paused), if indicated, but only after the intercurrent medical condition that precipitated the hypokalaemia has improved and K^+ has returned to the target range of normal levels (3.5 to 5.0 mmol/L, inclusive). The investigator will consider re-starting SZC with a lower dose.

If participant temporarily (≤ 14 days) discontinues study intervention for reasons other than hypokalaemia, SZC administration can be resumed once participant condition is stabilised according to investigator judgement, and if the participant is willing to take treatment.

Any time study drug dose is adjusted, or if a concomitant medication which may affect K^+ levels is changed (eg, use of RAASi or diuretics), the participant needs to return to the site 7 (± 2) days later for a K^+ measurement and recording of AEs and concomitant medications.

7.2 Participant Withdrawal from the Study

- A participant may withdraw from the study at any time at his/her own request, or may be withdrawn at any time at the discretion of the investigator for safety, behavioural, compliance, or administrative reasons. This is expected to be uncommon.

- A participant who considers withdrawing from the study must be informed by the investigator about modified follow-up options (eg, telephone contact, a contact with a relative or treating physician, or information from medical records).
- At the time of withdrawal from the study, if possible, an early study intervention discontinuation visit should be conducted, as shown in the SoA ([Table 1](#)). See SoA for data to be collected at the time of study withdrawal and follow-up and for any further evaluations that need to be completed.
 - The participant will discontinue the study intervention and be withdrawn from the study at that time.
- If the participant withdraws consent for disclosure of future information, the sponsor may retain and continue to use any data collected before such a withdrawal of consent.
- If a participant withdraws from the study, it should be confirmed if he/she still agrees for existing samples to be used in line with the original consent. If he/she requests withdrawal of consent for use of samples, destruction of any samples taken and not tested should be carried out in line with what was stated in the informed consent and local regulation. The investigator must document the decision on use of existing samples in the site study records and inform the Global Study Team.

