6.6 Study Intervention Compliance

When participants are dosed at the site, which will occur during the inpatient phase, they will receive SZC directly from the investigator or designee, under medical supervision. The date, and time if applicable, of dose administered in the hospital will be recorded in the source documents and recorded in the eCRF. The dose of SZC and study participant identification will be confirmed at the time of dosing by a member of the study site staff other than the person administering the study intervention.

When participants self-administer study interventions at home (SZC or SoC), compliance with study interventions will be assessed at each visit (both on-site and telephone visits).

Compliance will be assessed by counting returned sachets and direct questioning during the visits and documented in the source documents and eCRF. Deviation(s) from the prescribed dosage regimen should be recorded in the eCRF and in the source documentation.

A record of the number of SZC sachets for SZC dispensed to and taken by each participant must be maintained and reconciled with study intervention and compliance records. Intervention start and stop dates, including dates for intervention delays and/or dose reductions or increases will also be recorded in the eCRF.

There will not be accountability for participants allocated to SoC.

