7.3 Lost to Follow-up

A participant will be considered lost to follow-up if he or she repeatedly fails to return for scheduled visits and no contact has been established by the time the study is completed (see [Section 4.4](#)), such that there is insufficient information to determine the participant's status at that time.

Participants who decline to continue participation in the study, including telephone contact, should be documented as ‘withdrawal of consent’ rather than ‘lost to follow-up’. Investigators should document attempts to re-establish contact with missing participants throughout the study period. If contact with a missing participant is re-established, the participant should not be considered lost to follow-up and evaluations should resume according to the protocol.

The following actions must be taken if a participant fails to return to the clinic or to answer a phone call for a required study visit:

- The site must attempt to contact the participant and reschedule the missed visit as soon as possible and counsel the participant on the importance of maintaining the assigned visit schedule and ascertain whether or not the participant wishes to and/or should continue in the study.
- Before a participant is deemed lost to follow-up, the investigator or designee must make every effort to regain contact with the participant (where possible, 3 telephone calls and, if necessary, a certified letter to the participant's last known mailing address or local

equivalent methods). These contact attempts should be documented in the participant's medical record.

Discontinuation of specific sites or of the study as a whole are handled as part of [Appendix A](#).

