### 4.2.2.3 Handling of Dropouts and Missing Data

Participants who die prior to 180 days post-discharge, who are missing an assessment at visit 10 or who are lost to follow-up for any reason will be considered to be non-response for the primary analysis.

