#### **4.2.3.2 Derivations**

Time to first occurrence will be defined as the earliest date of (all-cause hospital admission, ED visits with HK as a contributing factor, all-cause death, use of rescue therapy for HK, date of loss to follow-up, date of 180 days post-discharge) – date of randomization + 1.

Risk Difference (RD) is calculated using the Austin method (Austin et al; 2010). First, the predicted probability of survival for each participant at 180 days post-discharge is calculated assuming that all participants do not receive SZC (Cmean). Second, the predicted probability of survival for each participant at 180 days post-discharge is calculated assuming that all participants receive SZC (Tmean). The RD is calculated as Tmean-Cmean. The 95% confidence interval will be calculated by taking the 2.5th and 97.5th percentiles of RDs across 1000 bootstrap samples where each bootstrap sample is drawn randomly with replacement from the original sample, such that the new sample is of the same size as the original sample.

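### The SAP endpoint rules do not name study withdrawal, so an early-discontinuation K+ from Days 136-173 can count as a Day-180 response and follow-up time can run on to Day 180

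*Protocol*

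**What the plan says.** **Leaving treatment and leaving the study.** Protocol 7.1.1 treats stopping the drug as something that does not end participation: "If study intervention is permanently discontinued, the participant will be followed up according to the SoA". Its reasons include an adverse event judged to put the participant at undue risk, and severe noncompliance. Protocol 7.2 then provides for study withdrawal, at the participant's request or because the participant "may be withdrawn at any time at the discretion of the investigator for safety, behavioural, compliance, or administrative reasons". It adds "This is expected to be uncommon" and asks for an E/D visit where possible. The Schedule of Activities and Protocol 8.1.1 include a central K+ at that visit.

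**How leaving is classified.** Protocol 7.3: "Participants who decline to continue participation in the study, including telephone contact, should be documented as" a withdrawal of consent, and not as a loss to follow-up. It does not classify an investigator's decision to withdraw someone.

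**Primary endpoint.** SAP 4.2.2.3 covers participants who die before Day 180 and those "who are missing an assessment at visit 10 or who are lost to follow-up for any reason will be considered to be non-response". SAP 3.3.1.4.1 also treats missing primary data as non-response. SAP Table 3 maps every K+ from Day 136 to Day 186 to Visit 10, against a protocol window of Days 174 to 186. SAP 3.3.2 takes the worst value in a window.

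**Other endpoints.** The time-to-event derivation in SAP 4.2.3.2 takes the earliest of the event dates and a list ending "use of rescue therapy for HK, date of loss to follow-up, date of 180 days post-discharge". SAP 4.2.4.2, 4.2.6.2 and 4.2.7.2 follow the same pattern. The negative binomial offset in SAP 4.2.5.4 stops at loss to follow-up or Day 180, whichever is first.

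**The concern.** The composite strategy for the primary endpoint is plainly meant to make a failure of anyone who does not reach Day 180. Because withdrawal is recorded as something other than loss to follow-up, whether a withdrawn participant fails depends on whether a K+ happens to fall in the Visit 10 window. An in-range E/D sample on Day 140, with no rescue therapy and no RAASi down-titration, is scored as normokalaemia at 180 days although the participant had left 40 days earlier.

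On the secondary endpoints, a withdrawn participant has no stopping date before Day 180 if the lists are applied as written. Unobserved time is then counted as event-free time at risk.

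The overlap between Protocol 7.1.1 and 7.2 adds to this. For the same safety or compliance event, one site may stop the drug and keep collecting the Day-180 K+ and admissions, while another ends participation. The primary estimand uses K+ after treatment discontinuation, so the second choice loses data that the estimand needs.

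**Working it through.** **Planned figures used as inputs (Protocol 9.2.1, 9.2.2, 4.1).** Normokalaemia 0.88 (SZC) and 0.59 (SoC); event-free proportions 0.83 and 0.568; 20% drop-out after randomisation. The plan's figures reproduce: HR = ln(0.83)/ln(0.568) = 0.329, and 104/0.8/0.8 = 162.5, so 163 enrolled. About 130 are randomised, 65 per arm, which gives 65 × 0.20 = 13 drop-outs per arm. None of these figures is disputed.

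**Who is caught and who is not, primary endpoint.**
- Last K+ before Day 136: no Visit 10 value, so non-response under SAP 4.2.2.3.
- E/D K+ on Days 136-173: inside the Table 3 window but before the protocol window. If in range and the only value in the window, it can count as a response.
- Table 3 does govern the primary endpoint: SAP 4.2.2.5 adds a sensitivity analysis whose stated difference is that windowing is dropped.

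**How many.** Assume drop-out is uniform over 180 days (the documents give no timing). Days 136-180 are 45/180 = 25% of the period, so 13 × 0.25 = 3.25 per arm. Days 136-173 alone are 38/180 = 21.1%, or 2.7 per arm. Either way the maximum is about 3, if every drop-out is a withdrawal with an E/D sample. If half are, 3.25 × 0.5 = 1.6 per arm; if a quarter, 0.8.

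**Effect on the primary difference, both arms affected, all drop-outs withdrawals.**
- All drop-outs non-responders: 0.8 × 0.88 = 0.704 and 0.8 × 0.59 = 0.472; difference 23.2 points.
- Those in Days 136-180 contribute at the planned rates: (0.8 + 0.2 × 0.25) × 0.88 = 0.748 and 0.85 × 0.59 = 0.5015; difference 24.65 points.
- Shift: 1.45 points. With Days 136-173 only: 0.2 × 0.211 × 0.29 = 1.2 points.

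**Effect on the main secondary endpoint.** Assume exponential event times, a fraction w withdrawing uniformly over 180 days, and withdrawn participants run event-free to Day 180. With S the true event-free proportion and λ = −ln(S), the apparent event-free proportion is (1 − w)S + w(1 − S)/λ. The term (1 − S)/λ is 0.17/0.1863 = 0.912 for SZC and 0.432/0.5656 = 0.764 for SoC.

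| Withdrawal, SZC / SoC | Apparent event-free, SZC / SoC | Ratio of logs (true 0.329) | Same calculation with no treatment effect |
|---|---|---|---|
| 20% / 20% | 0.846 / 0.607 | 0.334 | 1.00 |
| 20% / 5% | 0.846 / 0.578 | 0.304 | 0.91 |

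The last column uses S = 0.568 in both arms: ln(0.607)/ln(0.578) = 0.91. With equal 20% withdrawal the ratio barely moves, but absolute risks are understated: SoC 43.2% becomes 39.3% and SZC 17.0% becomes 15.4%. Ignoring events, time at risk per participant becomes 180 days instead of 0.8 × 180 + 0.2 × 90 = 162, an excess of 11%. That excess enters the count-model offset.

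**Checks on drop-out share the gap.** The completers analysis (SAP 4.2.2.5) removes only deaths and losses to follow-up. The inverse probability weighting model (SAP 4.2.3.5) codes only lost against not lost, so a withdrawn participant would be weighted as fully observed.

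**The case against.** The best defence is that the text already handles most of this.

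- The missing-Visit-10 rule catches any withdrawal with no K+ from Day 136 on, which is 75% under uniform timing. A reader might infer that withdrawn participants generally escape the non-response rule; they do not. This stands.
- The worst-value rule limits the remainder, but only when a second value falls in the window.
- The analysis without windowing is a partial check. It is restricted to Visit 10 K+ while the participant remains on SZC, which does not fit the SoC arm.
- Loss to follow-up for any reason could be read to include withdrawal. SAP 3.3.1.2 ends the outpatient period at withdrawal of consent, and SAP 4.2.3.3 takes the censoring date from the disposition form. So the SAP is ambiguous rather than plainly permissive. Protocol 7.3 nevertheless points the other way, and the endpoint derivations do not refer to the period definition.
- The Day-140 problem comes from the width of Table 3. Rewriting Protocol 7.2 alone would not remove it.

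A reader might also infer that withdrawals fall mainly on the SZC arm, since "There will not be accountability for participants allocated to SoC". The same section has compliance assessed at every visit for home treatment in both arms, and no figure in the documents supports an imbalance. The 20% against 5% row above is therefore an illustration, not an expectation. Even there, 0.91 under no effect is small: about 65 × (0.393 + 0.422) = 53 events give a standard error of 2/√53 = 0.27 for the log hazard ratio, and ln(0.91) = −0.09 is about a third of that.

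**Conclusion.** The point holds as a gap in the SAP. Applied as written, the rules can score a participant who has left the study as normokalaemic at 180 days, and can keep withdrawn participants at risk to Day 180 in the time-to-event and count analyses.

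The likely size is modest: up to about 3 participants per arm in the Visit 10 window and a shift of about 1.5 points in the primary difference if both arms are affected. This assumes that the planned 20% drop-out consists entirely of withdrawals, evenly timed, each with an E/D sample. The protocol expects withdrawal to be uncommon and makes the E/D visit conditional on its being possible, so fewer is more plausible. If only the SZC arm gained, its response would rise by 0.2 × 0.25 × 0.88 = 4.4 points at that maximum, but the documents give no reason to assume one-sided gain. Material bias in the hazard ratio needs unequal withdrawal.

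The reason to act is that one event has two permissible codings in an open-label trial, and the remedy is cheap.

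The overlap between Protocol 7.1.1 and 7.2 is real for safety and compliance reasons. A reader might conclude that investigator withdrawal should be abolished. The documents do not support that: it would settle a question of clinical management and leave administrative withdrawals with no route.

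**What to change.** Protocol 9.4 allows SAP changes until database lock.

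1. In SAP 4.2.2.3, state that anyone who leaves the study for any reason, by their own or the investigator's decision, before the protocol Visit 10 window (Day 174) is a non-responder, and that an E/D K+ is not assigned to Visit 10.
2. In SAP 4.2.3.2, 4.2.4.2, 4.2.6.2 and 4.2.7.2, add the date of study withdrawal to the list and censor there.
3. In SAP 4.2.5.4, end the offset at that date. SAP 4.2.8.4 inherits the change.
4. Use the same definition of leaving the study in the completers and inverse probability weighting analyses.
5. Reconcile Protocol 7.1.1 and 7.2 for safety and compliance reasons, so that sites know when outcome follow-up continues. No clinical rule is proposed here.

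The cost is a few sentences in the SAP and a clarification in the protocol. Sample size is unchanged. Response in the SZC arm may come out slightly lower.
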